For studies that involve collaboration with non-JHSPH institutions, complete the chart below by describing the collaboration and the roles and responsibilities of each partner, including the JHSPH investigator. This information helps us determine what IRB oversight is required for each party. Complete the chart for all multi-collaborator studies.

Insert collaborator names and FWA numbers, if available. Note who will be “engaged” in human subjects research by filling in the following table:

	JHSPH		
For federally funded studies, collaborators' FWA	00000287		
Primary Grant/Contract Recipient			
Grant/Contract Subrecipient			
Hiring Data Collectors			

Training Data Collectors			
Obtaining Informed Consent and/or Identifiable Data			
Accessing/Analyzing Identifiable Data			
Overseeing storage, access and use of biospecimens			

COMPLETE THE FOLLOWING SECTIONS WHEN RELEVANT TO YOUR STUDY:

XI. Secondary Data Analysis of Existing Data:

A. Study Design:

1. Describe your study design and methods. The study design must relate to your stated aims/objectives.
2. Provide an estimated sample size and an explanation for that number.
3. Provide a brief data analysis plan and a description of variables to be derived.

B. Participants:

1. Describe the subjects who provided the original data and the population from which they were drawn.

Note: If you are receiving, accessing, or using data from a U.S. health care provider, the need for HIPAA review is likely. If you plan to bring identifiable health information from a foreign country to a U.S. covered entity (e.g., lab at the Hopkins SOM), HIPAA may be triggered. If either of these conditions is met, check "yes" to the HIPAA question in the PHIRST application.

2. If you plan to analyze human specimens or genetic/genomic data, provide details about the source of those specimens and whether they were collected using an informed consent document. If yes, explain whether your proposed use is "consistent with" the scope of the original consent, if it potentially introduces new analyses beyond the scope of the original consent, and/or if it introduces new sensitive topics (HIV/STDs, mental health, addiction) or cultural/community issues that may be controversial.

3. Explain whether (and how) you plan to return results to the participants either individually or as a group.

XII. Oversight Plan for Student-Initiated Studies:

- A. For student-initiated studies, explain how the PI will monitor the student's adherence to the IRB-approved research plan, such as communication frequency and form, training, reporting requirements, and anticipated time frame for the research. Describe who will have direct oversight of the student for international studies if the PI will not personally be located at the study site, and their qualifications.
- B. What is the data custody plan for student-initiated research? *(Note: Students may not take identifiable information with them when they leave the institution.)*

XIII. Creation of a Biospecimen Repository:

Explain the source of the biospecimens, if not described above, what kinds of specimens will be retained over time. Clarify whether the specimens will be obtained specifically for repository purposes, or will be obtained as part of the core study and then retained in a repository.

- A. Describe where the biospecimens will be stored and who will be responsible for them.
- B. Describe how long the biospecimens will be stored, and what will happen at the end of that period.
- C. Explain whether the biospecimens will be shared with other investigators, inside and outside of JHU, how the decision to share will be made, and by whom. Include your plans, if any, for commercial use. Also explain how downstream use of the specimen will be managed, and what will happen to left-over specimens.
- D. Describe whether future research using the biospecimens will include specimen derivation and processing (cell lines, DNA/RNA, etc.), genomic analyses, or any other work which could increase risk to participants. Explain what additional protections will be provided to participants.
- E. If future research could yield unanticipated incidental findings (e.g., an unexpected finding with potential health importance that is not one of the aims of the study) for a participant, do you intend to disclose those findings to the study participant? Please explain your position.
- F. Explain whether the specimens will be identifiable, and if so, how they will be coded, who will have access to the code, and whether the biospecimens will be shared in linked (identifiable) form.

- G. Explain whether the repository will have Certificate of Confidentiality protections.
- H. Explain whether a participant will be able to withdraw consent to use a biospecimen, and how the repository will handle a consent withdrawal request.
- I. Describe data and/or specimen use agreements that will be required of users. Provide a copy of any usage agreement that you plan to execute with investigators who obtain biospecimens from you.

XIV. Data Coordinating Center:

Complete if JHSPH serves as the Data Coordinating Center.

- A. How will the study procedures be developed?
- B. How will the study documents that require IRB approval at each local site be developed? Will there be some sort of steering or equivalent committee that will provide central review and approval of study documents, or will template consent forms, recruitment materials, data collection forms, etc. be developed by and provided to the local sites by the coordinating center without external review?
- C. Will each local clinical site be overseen by its own IRB with an FWA, or will a Single IRB review the study? State whether the coordinating center will collect IRB approvals and renewals from the clinical centers; if not, explain why.
- D. How will the coordinating center provide each local site with the most recent version of the protocol and other study documents? What will be the process for requesting that these updates be approved by local clinical center IRBs?
- E. What is the plan for collecting data, managing the data, and protecting the data at the coordinating center?
- F. What is the process for reporting and evaluating protocol events and deviations from the local sites? Who has overall responsibility for overseeing subject safety: the investigators at the recruitment site, the Coordinating Center, the Steering Committee, or a Data and Safety Monitoring Board (DSMB)? Is there a DSMB that will evaluate these reports and provide summaries of safety information to all the

reviewing IRBs, including the coordinating center IRB? Please note that if there is a DSMB for the overall study, then the coordinating center PI does not have to report to the coordinating center IRB each individual adverse event/problem event that is submitted by the local site PIs.

- G. Some FDA regulated studies have different AE reporting criteria than that required by the IRB (IRB Policy No. 103.06). How will you reconcile the different requirements, and who is responsible for this reconciliation?
- H. Who is responsible for compliance with the study protocol and procedures and how will the compliance of the local sites be monitored and reviewed? How will issues with compliance be remedied?

XV. Drug Products, Vitamins, Food and Dietary Supplements:

Complete this section if your study involves a drug, botanical, food, dietary supplement or other product that will be applied, inhaled, ingested or otherwise absorbed by the study participants. If you will be administering drugs, please upload the product information.

- A. List the name(s) of the study product(s), and the manufacturer/source of each product.

Name of Study Product	Manufacturer/Source

- B. List each study product by name and indicate its approved/not approved status.

Approved by the FDA and Commercially Available	Approved by Another Gov't Entity (provide name)	Cleared for Use at Local Study Site

- C. If your study product has an Investigational New Drug (IND) application through the U.S. Food and Drug Administration, provide the IND number, and the Investigators Brochure.

- D. If your study product is a marketed drug, provide the package inserts or other product information. If the study product WILL NOT be used for its approved indication, dose, population, and route of administration, provide a detailed rationale justifying the off-label use of the study product.

- E. If the study product does not require FDA approval (e.g., dietary supplements, botanicals, products not subject to the U.S. FDA, etc.), provide safety information (as applicable) and a certificate of analysis.
- F. Explain who will be responsible for drug management and supply, labeling, dispensing, documentation and recordkeeping. Complete and upload into PHIRST the Drug Data Sheet available on the JHSPH IRB website at www.jhsph.edu/irb.
- G. What drug monitoring and/or regulatory oversight will be provided as part of the study?

XVI. Medical Devices:

Complete this section if your study will involve an approved or investigational medical device (**diagnostic**, non-significant risk, significant risk).

- A. List the name(s) of the study product(s), the manufacturer/source of each product, and whether or not it is powered (electric, battery). Provide product information. If it is electric, upload documentation of clinical engineering approval or its equivalent from a local authority, to ensure that the device is in good working order.

Name of Study Product	Manufacturer/Source	Powered?

- B. List each study product by name and indicate its status as approved by a government authority or not approved.

Approved by the FDA and Commercially Available	Approved by Another Gov't Entity (provide name and approval information)	Not Approved

- C. If your investigational device is Exempt from the FDA IDE regulations, explain which section of the code applies to your device and why it meets the criteria provided. If it is a **diagnostic device**, provide pre-clinical information about the sensitivity and specificity of the test and the anticipated failure rate. If you plan to provide the results to participants or their physicians, justify doing so, and explain how those results will validated (or not) against the current “gold standard”.
- D. If you believe the investigational device is not IDE exempt under 21CFR 812.2(c), but is a “Non-Significant Risk” device considered to have an approved IDE application, provide information from the manufacturer supporting that position.
- E. If you are using an investigational device that is a Significant Risk Device, provide the IDE number given by the FDA, or if not under FDA jurisdiction, explain why it is appropriate to use this device in this study. Provide a description of the device, and upload a picture or manufacturing schematics into PHIRST. Provide any other information relevant to a determination of its safety to be used for the purposes outlined in this research plan.

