Aim 1: A sample size of 80 participants receiving 3 randomized messages per day for 30 days will provide 7,200 observations. Across person-days, there will be an average of one prompt per day for each of the 3 conditions CBT, Mindfulness/ACT, and control (balance across person-days). Power estimations were conducted using an online tool specifically developed for sample size calculations for micro-randomized trials by consultant [name]. Assuming a message randomization probability of 1/3 (33% CBT, 33% Mindfulness/ACT, 33% control), a quadratic effect over time (initially smaller as participants are getting used to the intervention, increasing over time to peak at day 20, and decreasing thereafter as participants may get desensitized), and an average compliance rate of 75%, linearly decreasing over time, a sample size of N=80 participants will allow for detecting a standardized mean difference between CBT, Mindfulness/ACT, and control conditions on the primary outcome self-reported smoking urge of $d=0.1$ with a power of 0.8 and an alpha level of 0.05. This measure of effect size is a generalization of Cohen's d (standardized mean difference), with the difference that the standardization is by the average standard error over the entire study, with multiple treatments for each person. A Cohen's d of 0.1 is considered a small effect. A previous EMA study found that playing Tetris (analogous to a CBT distraction technique) decreased substance use urges with a mean effect size of $f^2=0.12$ (medium sized effect). Given these effect sizes in the existing literature, we will be adequately powered to detect effects in Aim 1 analyses.

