Aim 2: This aim will test between group differences in number of cigarettes smoked over time among micro-randomized trial (N=80) and EMA-only control group participants (N=80). Sample size calculations were based on findings from a recent app-based mindfulness meditation trial for smoking reduction. This trial only delivered intervention content for 14 days (as opposed to the 30 days proposed here) and found a significant reduction in 3.8 cigarettes/day in the intervention group compared to an increase in 0.8 cigarettes/day in the control group, which translates to an effect size of $d=0.651$ ($f=0.326$). Power estimation for between group repeated measures ANOVA and interactions were conducted with G-Power. Assuming an alpha level of 0.05, a sample size of N=160 will allow us to detect effects in reduction of cigarettes per day of $f=0.326$ and larger with a power of 0.80. Multiple imputation will be used for missing data and the full sample will be analyzed.

IV. Participants:

Describe the study participants and the population from which they will be drawn. Specify the inclusion and exclusion criteria. If you plan to include children, note their ages and whether you will include children in foster care. Note if the participants are particularly vulnerable in terms of cognitive limitations, education, legal migration status, incarceration, poverty, or some combination of factors.

A. Inclusion Criteria:

Participants will be young adult men and women who: 1) live in the U.S.; 2) read English; 3) are between 18 and 30 years of age; 4) own a smartphone with iOS and Android operating system and GPS capabilities; 5) are carrying their smartphone with them every day; 6) are willing to participate in the study for 44 days and give the research team access to the phone GPS data; 7) have smoked ≥ 100 cigarettes in their lives and currently smoke at least 1 cigarette per day on 3 or more days of the week (full trial: smoke at least 3 cigarettes per day on 5 or more days of the week); 8) are planning to quit smoking within the next 30 days.

B. Exclusion Criteria:

There are no additional exclusion criteria for participants that meet inclusion criteria.

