Aim 2 analyses will use data from both the micro-randomized trial group (N=80) and the EMA control group (N=80). **Primary outcome:** The primary outcome will be self-reported number of cigarettes/day in the past week at 45-day, 3-, and 6-month follow-up. GEE will examine cigarettes/day at each follow up by group (micro-randomized trial vs. EMA-only control). Independent variables are group membership, variables that differ by group at baseline, gender, and nicotine dependence. Again, **multiple imputation procedures** will be used to impute missing data at follow-up.

Analytical strategy Aim 3: Explore moderation effects of substance co-use (cannabis, alcohol, other drugs) and exposure to specific location (home, work, bars) on urge reduction message efficacy.

Based on our data on high co-use of cigarettes with cannabis and alcohol, as well as changes in perceived reward of smoking cigarettes when under the influence of cannabis or alcohol, analyses in this aim will explore if message efficacy is moderated by substance co-use (whether a participant currently is under the influence of another substance, e.g., cannabis, alcohol, other drugs). Centered and weighted least squares

models¹⁵² similar to those for Aim 1 will be estimated with predictors intervention message type (CBT, Mindfulness/ACT, control), substance use (cannabis, alcohol, other drugs, none), and their interaction. Based on existing evidence on alcohol and cannabis co-use as barrier to cigarette smoking cessation, we hypothesize that intervention message efficacy will be reduced when participants are under the influence of another substance. However, analyses for this aim will enable us to explore if specific types of messages (CBT, Mindfulness/ACT, and subconstructs) are more helpful in co-use situations.

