Moreover, we will explore aspects of intervention message-situation fit. We will test if specific locations (e.g., home, work, bars) impact intervention message efficacy. Mixed models will be estimated containing the predictors intervention type (CBT, Mindfulness/ACT, control), location (home, work, bar, other locations), and their interaction. We will explore other situational characteristics and intervention message-situation fit based on affect, arousal, stress, and the presence of other smokers. We do not have specific hypotheses about moderation effects of location and other situational characteristics, but findings will inform future interventions using adaptive messages over time to improve intervention-message situation fit and intervention efficacy.

5. Answer the following if they are relevant to your study design:

- A. If the study has different arms, explain the process for assigning participants (intervention/control, case/control), including the sequence and timing of the assignment.

We will use stratified block randomization to assign participants into the micro-randomized trial intervention group (N=80) and EMA-only control group (N=80). The stratification variable known to robustly impact smoking cessation success will be level of nicotine dependence (smoking within first 30 mins after waking, y/n).¹³¹ Gender will be used as additional stratification variable. We will generate a randomization table and participants will be assigned after baseline completion.

- B. If human biospecimens (blood, urine, saliva, etc.) will be collected, provide details about who will collect the specimen, the volume (ml) and frequency of collection, how the specimen will be used, stored, identified, and disposed of when the study is over. If specimens will be collected for use in future research (beyond this study), complete the “Biospecimen Repository” section below.

N/A

- C. If genetic/genomic analyses are planned, address whether the data will be contributed to a GWAS or other large dataset. Address returning unanticipated incidental genetic findings to study participants.

N/A

- D. If clinical or laboratory work will be performed at JHU/JHH, provide the JH Biosafety Registration Number.

N/A

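### Aim 2 power statement is wrong as written: 160 participants give about 98% power at f = 0.326, not 0.80, and 80% power is reached near d = 0.45

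*Combined protocol and SAP*

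**What the plan says.** Section III.B (Aim 2) takes its planning effect from an earlier app-based mindfulness trial: a fall of 3.8 cigarettes per day against a rise of 0.8, "which translates to an effect size of $d=0.651$ ($f=0.326"). It names the method: "Power estimation for between group repeated measures ANOVA and interactions were conducted with G-Power". It then concludes that "N=160 will allow us to detect effects in reduction of cigarettes per day of $f=0.326$ and larger with a power of 0.80", at alpha 0.05. No attrition rate is given; missing data are to be multiply imputed and everyone analysed.

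Three other places bear on this:

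- Section III.B (Aim 1) sizes the micro-randomized arm separately: "a sample size of N=80 participants will allow for detecting a standardized mean difference" of d = 0.1 with power 0.8.
- Section V.C.5.A assigns participants to the "micro-randomized trial intervention group (N=80) and EMA-only control group (N=80").
- Section V.C.4 (Aim 2) gives the planned analysis: "GEE will examine cigarettes/day at each follow up by group (micro-randomized trial vs. EMA-only control"). The follow-ups are at 45 days, 3 months and 6 months.

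**The concern.** The sentence presents f = 0.326 as the lower limit of what 160 participants detect with 80% power. A standardized difference of 0.651 is large for 80 per arm, so power there should be well above 0.80. Either the power, the effect or the sample size does not belong with the other two.

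This is the only power statement for the Aim 2 primary outcome. Taken at face value, it says that effects below d = 0.651 fall under 80% power. The planning effect rests on one earlier trial, so what the study can detect if the true effect is smaller is the useful information, and the sentence gets it wrong. Nor does the text say whether the 0.80 belongs to the between-group test or to the interaction.

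**Working it through.** **Inputs from section III.B (Aim 2).** f = 0.326, d = 0.651, alpha 0.05, 80 per arm (N = 160), stated power 0.80. For two equal groups f = d/2 = 0.651/2 = 0.3255, so the two effect sizes agree. The follow-up times come from section V.C.4. Number of measurements (m), correlation (ρ), sphericity correction (ε) and attrition are not stated for the calculation; values used for them below are assumptions.

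**Attempt to reproduce 0.80, one follow-up.** Noncentral F with λ = f²N and 1 and N − 2 degrees of freedom:

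- λ = 0.326² × 160 = 0.106276 × 160 = 17.00
- critical F(1, 158) at 0.05 = 3.90
- power = 0.984, against the stated 0.80

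**Repeated-measures, between-group test.** λ = f²Nm / [1 + (m − 1)ρ], 1 and 158 degrees of freedom. For m = 3:

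| ρ (assumed) | λ | Power |
|---|---|---|
| 0.5 | 25.51 | 0.999 |
| 0.7 | 21.26 | 0.996 |
| 0.9 | 18.22 | 0.989 |
| 1.0 | 17.00 | 0.984 |

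The single-follow-up figure is the floor, reached at ρ = 1. With m = 4 (baseline counted), power at ρ = 0.9 is 0.989 and the floor is the same.

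**Interaction test.** λ = f²Nmε / (1 − ρ). The least favourable case with ρ from 0 upwards is ρ = 0 with lower-bound ε = 1/(m − 1):

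- m = 3: λ = 17.00 × 3 × 0.5 = 25.51, power 0.999
- m = 4: λ = 17.00 × 4 / 3 = 22.67, power 0.997

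**Other ways power could be lower.**

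- Alpha split over three follow-ups (0.05/3, not in the plan): 0.955.
- 20% of outcomes missing (assumed; N = 128, λ = 13.60): 0.955.
- 30% missing (assumed; N = 112, λ = 11.90): 0.928.

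**N that gives 0.80 at f = 0.326, one follow-up.** N = 76 (λ = 8.08) gives 0.801 and N = 78 (λ = 8.29) gives 0.811. In these single-comparison terms, 160 would be right only if 1 − 78/160 = 51% to 1 − 76/160 = 53% of outcomes were missing.

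**Effect that 160 detects with 80% power, one follow-up.** Solving for f, with d = 2f:

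| N analysed | f | d |
|---|---|---|
| 160 | 0.2228 | 0.446 |
| 128 (20% missing, assumed) | 0.2495 | 0.50 |
| 112 (30% missing, assumed) | 0.2671 | 0.53 |

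With complete data, 0.446/0.651 = 0.685, so the detectable effect is about 31% smaller than the one stated. A between-group test over m = 3 or 4 with ρ from 0.5 to 0.9 lowers it further, to d between 0.35 and 0.43.

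**The case against.** The best defence has four parts.

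*The sentence is true if read as at least 0.80.* That is so, and the trial is adequately powered for its planning effect. But the words "of $f=0.326$ and larger with a power of 0.80" set f = 0.326 as a threshold, and Aim 1 words its own detectable effect in a similar way, so the same reading is natural here. As a bare minimum the sentence would say little about sensitivity.

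*The 160 may come from Aim 1 rather than from this calculation.* This is plausible: Aim 1 needs 80 in the micro-randomized arm, and equal allocation doubles it. It explains the sample size but not the 0.80. An inherited N calls for reporting the power that it gives.

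*G-Power may have been run with other settings.* If the interaction noncentrality is taken as f²Nε, without the m/(1 − ρ) factor, power is 0.83 for m = 3 with ε = 0.5; for m = 4 it runs from 0.66 (ε = 1/3) to 0.946 (ε = 1) and passes 0.80 near ε = 0.54. So 0.80 can be reached without missing data, but only by assuming both that form and a particular ε. Nothing in the documents supports either. What stands is that the missing inputs matter: an undisclosed choice could move the answer this much.

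*The replacement figures are for one unadjusted comparison with complete data, whereas the analysis is a GEE with covariates and imputation.* This is correct, and the figures should carry that label. A comparison by group at each follow-up is nevertheless what section V.C.4 describes, so the single-comparison figure is relevant.

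It is also fair that not every input is missing: alpha, effect size, N, target power and test family are given.

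**Conclusion.** The point holds. At N = 160, f = 0.326 and alpha 0.05, power is 0.984 for one follow-up, at least that for a between-group repeated-measures test, and at least 0.997 for the interaction test in its usual form. The stated 0.80 is therefore a wrong power figure for the stated effect and sample size. The effect with 80% power is d = 0.446 (f = 0.223), and f = 0.326 would need about 76 to 78 participants in total.

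The 0.984 and 0.446 assume equal arms, a two-group F test at one follow-up and complete data. With an assumed 20 to 30% missing, power at f = 0.326 is still 0.955 to 0.928. The error understates the trial's sensitivity; it does not threaten the sample size. It concerns the full trial and should be corrected, but does not call the design into question.

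**What to change.** Keep N = 160 and rewrite the Aim 2 power sentence in section III.B to say:

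- 80 per arm gives about 98% power for d = 0.651 (f = 0.326), and 80% power for d of about 0.45 (f of about 0.22), at one follow-up with complete data;
- the effect detectable with 80% power under a stated attrition assumption, for example d of about 0.50 with 20% missing or 0.53 with 30% missing;
- the G-Power inputs: which test the power refers to (between-group or interaction), number of measurements, correlation among them, any sphericity correction and effect-size convention, and attrition.

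If 160 was set by Aim 1 and equal allocation, one clause saying so would make the reasoning clear. The cost is one or two rewritten sentences, with no change to enrolment, design or analysis.
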